6.7.7.3. Baseline Attack Rate

The baseline attack rate will be calculated using data from the SOC period and standardized to number of attacks per month, where 1 month is defined as a 28-day (4 week) period. It is calculated as:

$$\frac{\text{Number of HAE attacks during the SOC period Screening} * 28}{\text{Study Day 1 Date} - \text{Screening Date} + 1}$$

where the number of HAE attacks during SOC period includes any attacks starting after informed consent through the time of first dose. The screening day is the first day of the SOC period. Note that the SOC period starts upon signing the informed consent form. A similar method will be used to calculate other baseline rates (eg, baseline HAE attacks treated with rescue medication).

6.7.7.4. Attack Rate in Parts 1 and 2

The observed attack rate will be computed as the number of attacks per month, where 1 month is defined as a 28-day (4-week) period.

In general, the formula for computing an attack rate is the number of attacks meeting the attack criteria divided by the duration of the reporting period of interest.

$$\text{Attack Rate} \left(\frac{\text{attacks}}{\text{month}} \right) = \frac{\text{Number of Attacks} * 28}{\text{Duration of Treatment Period of Interest}}$$

For subjects who complete the reporting period of interest, duration of reporting period of interest is defined as the last day in the reporting period – first day in reporting period + 1. For subjects who discontinue treatment prematurely in the reporting period of interest, the duration of reporting period of interest is defined as (last day of treatment +1) – first day in reporting period + 1. For example, if a subject receives the last treatment on Day 13 of Month 3 with 2 attacks between Day 1 and Day 14, that subject will be considered to have had a rate of 4 attacks/month ($2 \times 28/14 = 4$) for Month 3. Both the reporting period and the treatment period have been adjusted to include an additional day as the subject prematurely discontinued dosing in Month 3.

Subject-Reported Attack Rate

Subject-reported attack rates will be computed through Week 12 and through Week 48 (eg, 0-12 weeks and 0-48 weeks).

Adjusted Attack Rate

Adjusted attack rates will be computed for the following reporting periods of interest and expressed in units of attacks/month where 1 month = 28 days:

- During SOC
- By month
- Through Week 12 (eg, 1-12 weeks)
- Through Week 48 (eg, 1-48 weeks)

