Adjusted attack rates will be calculated during the SOC period as well as study Parts 1 and 2. For on-study adjusted attack rates by month, months will be defined in blocks of 28 days, beginning on Day 1, after the first dose of berotralstat. If an attack occurs on Day 1, and the time of both the attack and berotralstat administration are recorded, then an attack prior to berotralstat should be counted in the SOC period and an attack after berotralstat administration should be counted in Week 1 (Month 1). Should a subject prematurely discontinue treatment at the end of the monthly reporting period (ie, Day 28), any attacks that occur within 24 hours after last dose will be counted in the calculation of attack rate of the prior month and the additional 24-hour period will be included in the duration of the reporting period. For example, if a subject has 1 attack from Day 1 to 28, discontinues drug on Day 28, and has an attack on Day 29, the Month 1 (Day 1 to Day 28) attack rate will be 0.55 attacks/month ($2 \times 28/29 = 0.55$). Since HAE attack data are only to be collected during SOC, Part 1, and Part 2, an attack that numerically falls beyond Week 48 will be included with data in Week 48 (Month 12) if it occurs on or prior to the Week 48 visit (also see Table 5).

No imputation will be done for missing data.

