X	X*		14.1.5.1.2	Treatment Exposure and Compliance During Weeks 1-12	Week 12 Completer
X	X		14.1.5.1.3	Treatment Exposure and Compliance During Weeks 1-48	Week 48 Completer
X	X	X	14.1.5.2	Plot of Duration of Exposure to Study Drug	Safety
X			14.2.1.1.1	Summary of Plasma BCX7353 Concentrations (ng/mL) at Week 2	PK
X			14.2.1.1.2	Summary of Plasma BCX7353 Concentrations (ng/mL) Following Dose Modifications	PK
X			14.2.1.2.1	Summary of BCX7353 PK Parameters (New table to be specified by PK group)	PK
X	X		14.2.2.1.1	Summary of HAE Adjusted Attack Rate	Safety
X	X		14.2.2.1.2	Summary of HAE Adjusted Attacks Rate After Week 2	Safety
X	X		14.2.2.1.3	Summary of HAE Adjusted Attack Rate, During Weeks 1-12	Safety
X	X		14.2.2.1.4	Summary of HAE Adjusted Attack Rate, During Weeks 1-48	Safety

NDA IA	End of Part 2 (Wk 48) IA†	Final/ EOS**	Output Number	Title	Population
X	X		14.2.2.1.5	Summary of HAE Adjusted Attack Rate, During Weeks 1-12	Week 12 Completer
X	X		14.2.2.1.6	Summary of HAE Adjusted Attack Rate, During Weeks 1-48	Week 48 Completer
X			14.2.2.1.7	Summary of HAE Adjusted Attack Rate during the SOC Period	Safety
X			14.2.2.2.1	Summary of HAE Adjusted Attacks	Safety
X	X		14.2.3.2.1	Mean HAE Adjusted Attack Rate by Month	Safety
X	X*		14.2.3.2.2	Mean HAE Adjusted Attack Rate by Month, During Weeks 1-12	Week 12 Completer
X	X		14.2.3.2.3	Mean HAE Adjusted Attack Rate by Month, During Weeks 1-48	Week 48 Completer
X	X		14.2.3.3.1	Summary of Duration of Adjusted Attacks (hours)	Safety
X	X*		14.2.3.3.2	Summary of Duration of Adjusted Attacks (hours), During Weeks 1-12	Week 12 Completer
X	X		14.2.3.3.3	Summary of Duration of Adjusted Attacks (hours), During Weeks 1-48	Week 48 Completer
X			14.2.3.4.1	Summary of Attack Characteristics for Adjusted Attacks During the SOC Period	Safety
X	X		14.2.3.4.2	Summary of Attack Characteristics for Adjusted Attacks	Safety
X	X*		14.2.3.4.3	Summary of Attack Characteristics for Adjusted Attacks, During Weeks 1-12	Week 12 Completer
X	X		14.2.3.4.4	Summary of Attack Characteristics for Adjusted Attacks, During Weeks 1-48	Week 48 Completer
X			14.2.3.5.1	Summary of Attack Locations for Adjusted Attacks During the SOC Period	Safety
X	X		14.2.3.5.2	Summary of Attack Locations for Adjusted Attacks	Safety
X	X*		14.2.3.5.3	Summary of Attack Locations for Adjusted Attacks During Weeks 1-12	Week 12 Completer
X	X		14.2.3.5.4	Summary of Attack Locations for Adjusted Attacks During Weeks 1-48	Week 48 Completer

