NDA IA	End of Part 2 (Wk 48) IA†	Final/ EOS**	Output Number	Title	Population
X			14.2.3.6.1	Summary of HAE Adjusted Attack Rate for Attacks Requiring Treatment with Targeted HAE Medications during the SOC Period	Safety
X	X		14.2.3.6.2	Summary of HAE Adjusted Attack Rate for Attacks Requiring Treatment with Targeted HAE Medications	Safety
X	X*		14.2.3.6.3	Summary of HAE Adjusted Attack Rate for Attacks Requiring Treatment with Targeted HAE Medications During Weeks 1-12	Week 12 Completer
X	X		14.2.3.6.4	Summary of HAE Adjusted Attack Rate for Attacks Requiring Treatment with Targeted HAE Medications During Weeks 1-48	Week 48 Completer
X	X		14.2.3.7.1	Mean HAE Adjusted Attack Rate for Attacks Requiring Treatment with Targeted HAE Medications by Month	Safety
X	X*		14.2.3.7.2	Mean HAE Adjusted Attack Rate for Attacks Requiring Treatment with Targeted HAE Medications by Month During Weeks 1-12	Week 12 Completer
X	X		14.2.3.7.3	Mean HAE Adjusted Attack Rate for Attacks Requiring Treatment with Targeted HAE Medications by Month During Weeks 1-48	Week 48 Completer
X	X		14.2.4.1.1	Summary of Number and Proportion of Days with Angioedema Symptoms from Adjusted Attacks	Safety
X	X*		14.2.4.1.2	Summary of Number and Proportion of Days with Angioedema Symptoms from Adjusted Attacks During Weeks 1-12	Week 12 Completer
X	X		14.2.4.1.3	Summary of Number and Proportion of Days with Angioedema Symptoms from Adjusted Attacks During Weeks 1-48	Week 48 Completer
X	X		14.2.5.1	Plot of Mean and Median Adjusted HAE Rate by Month	Safety
X	X*		14.2.5.2	Plot of Mean and Median Adjusted HAE Rate by Month During Weeks 1-12	Week 12 Completer
X	X		14.2.5.3	Plot of Mean and Median Adjusted HAE Rate by Month During Weeks 1-48	Week 48 Completer
X	X		14.2.5.4	Plot of Mean and Median Subject Reported HAE Rate by Month	Safety
X	X*		14.2.5.5	Plot of Mean and Median Subject Reported HAE Rate by Month During Weeks 1-12	Week 12 Completer

NDA IA	End of Part 2 (Wk 48) IA†	Final/ EOS**	Output Number	Title	Population
X	X		14.2.5.6	Plot of Mean and Median Subject Reported HAE Rate by Month During Weeks 1-48	Week 48 Completer
X			14.2.6.1	Summary of Average Number of Hospitalizations and Clinic Visits During the SOC Period	Safety
X	X		14.2.6.2	Summary of Average Number of Hospitalizations and Times Subject Sought Medical Care	Safety
X	X*		14.2.6.3	Summary of Average Number of Hospitalizations and Times Subject Sought Medical Care During Weeks 1-12	Week 12 Completer

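### By-month attack rates give a child with a two-day month the same weight as a child with a full month; adding an exposure-weighted rate beside the mean and median would steady small-cohort displays

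*SAP*

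**What the plan says.** SAP 6.7.7.4 computes a rate for each child: "the formula for computing an attack rate is the number of attacks meeting the attack criteria divided by the duration" of the reporting period, multiplied by 28. For the by-month view, "months will be defined in blocks of 28 days, beginning on Day 1". For a child who stops treatment early within a period, "the duration of reporting period of interest is defined as (last day of treatment +1) – first day in reporting period + 1". The SAP illustrates this with a child who has two attacks and a last dose on Day 13 of Month 3; "that subject will be considered to have had a rate of 4 attacks/month".

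These rates feed output 14.2.3.2.1, "Mean HAE Adjusted Attack Rate by Month", and output 14.2.5.1, "Plot of Mean and Median Adjusted HAE Rate by Month", both on the safety population. SAP 6.4 summarises continuous data by n, mean, SD or SEM, median, minimum and maximum. SAP 12.1 asks for summaries by cohort and for all subjects. SAP 8.5.1 keeps all available data from children who withdraw and imputes nothing. Neither the text nor the list of outputs in SAP Table 7 mentions a minimum exposure, an exposure weight, or a pooled rate (all attacks over all days at risk).

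**The concern.** A rate from two days and a rate from 28 days enter the same mean as if they carried equal information. Scaling two days up to a month multiplies whatever happened by 14, so a short partial month enters the cohort mean as either a very high value or zero. Minimum cohort sizes are 4, 4, 4 and 3, so one such child can set the monthly mean for a cohort.

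The schedule makes short partial months plausible. By SAP Tables 4 and 5, the Week 12, 24 and 36 target days (85, 169 and 253) are the first days of Months 4, 7 and 10. A child who takes a last dose on or just after one of those visits leaves a partial month of a few days. At stake is how the monthly course of attacks reads by cohort: a one-month spike or dip could come from a child observed for two days.

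**Working it through.** **The plan's own example.** Rate = attacks × 28 / duration, with duration = (last treatment day + 1) − first day + 1 for an early stopper. Last dose on Day 13 of the month: duration = (13 + 1) − 1 + 1 = 14 days; 2 × 28/14 = 4.0. This matches the SAP.

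The second example in the same section does not reproduce. It says that for two attacks in 29 days the Month 1 "attack rate will be 0.55 attacks/month", but 2 × 28/29 = 1.93. That is a separate slip and plays no part below.

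**Shortest month.** Last dose on Day 85: duration = (85 + 1) − 85 + 1 = 2 days, so one attack gives 1 × 28/2 = 14 attacks/month. Last doses on Days 86, 87 and 88 give 3, 4 and 5 days, so one attack gives 9.3, 7.0 and 5.6. The SAP's rule for a child who stops on Day 28 moves the extra day into the prior month and so avoids a one-day month. It does nothing for a stop one day later.

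**Effect on the cohort mean.** Assumptions: one child has one attack in two days, and each of the other n − 1 children has 28 days at rate r. The documents give no expected rate, so r is varied.

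- Simple mean = [(n − 1)r + 14] / n
- Exposure-weighted rate = [(n − 1)r + 1] × 28 / [28(n − 1) + 2]

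| n | r (per month) | Simple mean | Exposure-weighted |
|---|---|---|---|
| 4 | 0 | 3.50 | 0.33 |
| 4 | 0.5 | 3.88 | 0.81 |
| 4 | 1 | 17/4 = 4.25 | 4 × 28/86 = 1.30 |
| 4 | 2 | 5.00 | 2.28 |
| 3 | 1 | 16/3 = 5.33 | 3 × 28/58 = 1.45 |
| 30 | 1 | 43/30 = 1.43 | 30 × 28/814 = 1.03 |

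At n=4 and r=1 the one child supplies 14/17 = 82% of the summed rates. If that child has no attack, the mean is 3/4 = 0.75 and the weighted rate 3 × 28/86 = 0.98, so a short partial month can also pull the mean down.

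**Noise or bias.** Assume Poisson counts at 1/month for every child, with stopping unrelated to attacks. The chance of at least one attack in two days is 1 − exp(−2/28) = 6.9% (3.5% at 0.5/month, 13.3% at 2/month). The rate from a two-day month has SD √(28/2) = 3.74, against 1.00 for a full month. For n=4:

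- SD of the simple mean = √(3 × 1 + 14)/4 = 1.03
- SD of the exposure-weighted rate = √(3 + 2/28) × 28/86 = 0.57

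Both have expectation 1, so under this assumption the cost is variance only.

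**Period rates.** A child who stops on Day 29 with one attack in total has 30 days at risk, so the Week 1-12 or Week 1-48 rate is 28/30 = 0.93. A period rate of 14 from one attack requires a last dose on study Day 1.

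**The case against.** The strongest reply is that the plan already shows a reader what is needed. The median is reported and plotted beside the mean; in the illustration (14, 1, 1, 1) it is 1, and at n=3 (14, 1, 1) it is also 1. The maximum would show the 14, and listing 16.2.6.1.3 gives the individual rates. The by-month table and plot are repeated in Week 12 and Week 48 completers (outputs 14.2.3.2.2, 14.2.3.2.3, 14.2.5.2 and 14.2.5.3). The worst case needs both a stop at the start of a block and an attack within two days. Cohort sizes of 3 and 4 are minimums within about 30 planned children. Effectiveness is secondary and no hypothesis is tested. A mean of child-level rates and a pooled rate are both legitimate summaries, and pooling gives less weight to a child who stops because treatment failed.

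Most of this stands and limits the point. Two things remain. The completer displays leave out children who stop early, so they check the trend without them but do not estimate a rate that keeps them. The mean is still a headline statistic of the by-month outputs, without exposure days specified to show how much observation lies behind it.

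A reader might go further and infer that the by-month display is the main effectiveness result. SAP 3.2.2 and 12.1 define the endpoint windows as Week 1 through Weeks 12 and 48, with their own tables (14.2.2.1.3 to 14.2.2.1.6); the monthly view is additional.

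**Conclusion.** The point holds for the by-month rates, as a cheap improvement. As written, a monthly cohort mean can be driven by a child observed for two days: 4.25 against 1.30 in a cohort of four, 5.33 against 1.45 in a cohort of three, and 1.43 against 1.03 over 30 children. These figures assume one attack in the two-day month and 1 attack/month in the others. Equal weighting is inferred from the general summary rules in SAP 6.4; the SAP does not state it in so many words, and the table shells are in a separate document.

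Two stronger readings are tempting but not supported. One is that the monthly means are biased upward. That would require attacks to prompt stopping. Discontinuation for lack of efficacy is an endpoint, but nothing in the documents says that such stops follow an attack within days. The other is that the period rates share the distortion. They are also averages over children, but their denominators accumulate from Day 1, so they are little affected unless a child stops within the first days. No error rate or sample size is touched.

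**What to change.** In output 14.2.3.2.1 keep the mean and median and add, for each month, total attacks × 28 / total days at risk, by cohort and overall, with n and total exposure days. Show this rate on output 14.2.5.1 as an additional line, not as a replacement for the mean or median. State the formula in SAP 6.7.7.4.

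The cost is one extra rate row with its exposure days, and one extra line on a plot; no new data are needed. The downside is that the pooled rate gives less weight to children who stop early, including any who stop for treatment failure, so it should be read beside the mean and median. The 29-day worked example in the same section can be corrected in the same edit.

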6.7.7.5. Number and Proportion of Days with Angioedema Symptoms

The number of days with angioedema symptoms is the number of the days during the reporting period for which at least 1 symptom is reported during an adjusted HAE attack based on the start date and resolution date of an attack. The definition of the reporting period will be specified for subjects who discontinue in the same manner as for the attack rate calculation (see Section 6.7.7.4). with angioedema symptoms is derived as the number of days with angioedema symptoms divided by the duration of the reporting period of interest. The calculation will be performed similarly to the calculation of the attack rate (see Section 6.7.7.3).

6.7.7.6. Attack Duration

The duration of each subject-reported attack will be calculated in hours, based on the start, and stop date and time of the subject-reported attack (time the attack finished). For an adjusted attack that includes more than 1 subject-reported attack, the duration is calculated from the start of the

first subject-reported attack to the end of the last subject-reported attack that has been combined into 1 adjusted attack. Similarly, the duration of the attack from start of the attack to time that “the worst was over” will also be calculated.

All subject-reported attack durations will be included in listings and those included in adjusted attacks will be denoted. Adjusted attack duration will be summarized.

6.7.7.7. Medications to Treat HAE Attacks

The following medications reported taken as acute treatment in the subject diary will be classified in the analyses as targeted medications to treat subject-reported HAE attacks: Berinert[®], Cinryze[®], Kalbitor[®], Firazyr[®], Ruconest[®], and fresh frozen plasma.

All other medications also recorded in the subject diary as HAE treatments, will be classified as non-targeted medications: pain or anti-cramping medication, nausea medication, intravenous fluids, other.

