7.2. Subject Selection

7.2.1. Inclusion Criteria

Subjects must meet all of the following inclusion criteria to be eligible for participation in this study:

1. Male and non-pregnant, non-lactating females 2 to < 12 years of age and weighing ≥ 12 kg.
2. Parent/caregiver (P/C) willing and able to provide written, informed consent (with assent from the child where appropriate).
3. Subjects with a clinical diagnosis of HAE. A clinical diagnosis of HAE is defined as:
 - a. Screening results that document immunogenic C1-INH antigenic level below the lower limit of normal (LLN) reference range or C1-INH function $< 50\%$, and a complement 4 (C4) level below the LLN reference range.

OR

- b. Laboratory documentation of historical C1-INH functional level below the assay lower limit of normal.

OR

- c. For subjects with C1-INH function $\geq 50\%$ but less than the assay LLN, a SERPING-1 gene mutation known or likely to be associated with HAE Type I or II, as assessed during the screening period OR a repeat C1-INH functional level $< 50\%$ will be considered acceptable for enrollment.

OR

- d. Historical or new laboratory documentation of a SERPING-1 mutation known or likely to be associated with HAE.

OR

- e. For subjects who currently use plasma-derived or recombinant C1-INH based prophylactic therapies, a confirmed family history of C1-INH deficiency.
- 4. For subjects who are not currently receiving prophylaxis for HAE, documented history of ≥ 2 HAE attacks in the 6 months prior to the enrollment visit.
 - 5. Access to and ability to use one or more acute medications approved by the relevant competent authority for the treatment of acute attacks of HAE.
 - 6. In the opinion of the investigator, the subject would benefit from long term oral HAE prophylaxis.
 - 7. Females who had started their menses and males must either:
 - a. Be sexually abstinent. Abstinence in this study is defined as true abstinence: when this is in line with the preferred and usual lifestyle of the subject.
 - b. Use contraception. The following represents the minimum contraception that should be used by subjects who could be sexually active. Additional contraceptive requirements, such as highly effective methods, may be required by local site practice and/or governing institutional review board/ethics committee. It is anticipated that not all contraceptive methods may be available in all countries/regions, so the list should be modified accordingly.

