6.7.7.2. Adjusted Attack

Subject-reported attacks reported must meet the following criteria (applied in order) for inclusion in effectiveness analyses:

- Attack must include at least 1 symptom of swelling;
- Subject response to diary question, “In retrospect, could there be an alternative explanation for your symptoms other than an HAE attack (ie, allergic reaction, viral cold etc.)?” must be “no”.
- Attack must be unique (attack began > 24 hours from the end of the prior attack);
- Any attack that begins within 24 hours from the end of a prior attack will be combined with the prior attack;

- If the entire adjusted attack is untreated, it must have a duration > 24 hours.

Using the above criteria, adjusted attacks will be determined programmatically. For adjusted attacks that span 2 or more subject-reported attacks, attack triggers, locations, symptoms, duration, and other characteristics will be based on the information from each component subject-reported attack. Additionally, the start date/time of the adjusted attack will be the start date/time from the first attack and then end date/time of the adjusted attack will be the end date/time from the last attack being collapsed programmatically.

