9.6. HAE Medical and Medication History

HAE and HAE medication history will be summarized for the following where possible:

- HAE history
- Past on-demand treatments of HAE
- Current on-demand treatments of HAE
- Past prophylactic treatments of HAE

A summary of the HAE Medical History information as provided on the HAE Medical History page will be provided. A summary of screening complement 4 (C4), C1-INH antigen level, and functional C1 esterase inhibitor (C1-INHf) will be provided in categories showing how subjects met the inclusion criteria confirming diagnosis of HAE. Confirmation by SERPING1 gene mutation analysis, if required, will be included in the summary. Categories for C4 will be $C4 < \text{lower limit of normal (LLN)}$ and $C4 \geq \text{LLN}$ and for C1-INHf will be $< 50\%$, 50% to $< 74\%$, and $\geq 74\%$. Where the C4 test has been repeated, the test result for the repeat will be used in this summary.

Past prophylactic treatments will include those medications that were taken as prophylaxis and discontinued prior to the initiation of study treatment as recorded on the HAE Medication History Page. Past prophylactic medications will include Cinryze, Berinert, tranexamic acid, Takhzyro, HAEGARDA, and androgens. Androgens could include oxandrolone, danazol, and stanozolol.

Past on-demand treatments will include those medications that were taken as needed and discontinued prior to the initiation of study treatment as recorded on the HAE Medication History Page. Current on-demand medications will include those that are noted at screening as currently used for on-demand treatment as recorded on the HAE Medication History Page. Summaries of on-demand medications will include a grouping of any C1-INH medication as well as displays of individual medications. The C1-INH grouping will include plasma-derived C1-INH replacement (Firazyr, Cinryze on-demand, Berinert on-demand, Kalbitor) and recombinant C1-INH replacement (Ruconest). Fresh frozen plasma, a source of C1-INH, will also be considered an on-demand treatment and included with the plasma derived C1-INH replacements.

In addition, detailed SERPING data (laboratory confirmed or historically obtained) will be listed if provided.

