12.1.5. Use of HAE Medications

Use of targeted HAE medications as noted in the subject diary will be summarized separately from concomitant medications as noted in Section 6.7.7.7. In addition, summaries of the number of subject-reported HAE attacks requiring treatment will be provided.

The subject-reported and adjusted attack rates of attacks requiring treatment with targeted HAE medications will be summarized as noted in Section 6.7.7.7.

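### The targeted-treatment attack rates count only five brands plus fresh frozen plasma, a narrower set than the acute HAE medicines the protocol lets families use

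*SAP*

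**What the plan says.** SAP 6.7.7.7 names six items: Berinert, Cinryze, Kalbitor, Firazyr, Ruconest and fresh frozen plasma. When reported in the diary as acute treatment, these "will be classified in the analyses as targeted medications to treat subject-reported HAE attacks". It then sets the rule for the rest: "All other medications also recorded in the subject diary as HAE treatments, will be classified as non-targeted medications". The categories it gives for these are medicines for pain or cramps, medicines for nausea, intravenous fluids, and a catch-all 'other'. The list has no 'for example', no reference to active substance and no provision for equivalents.

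SAP 12.1.5 then plans the subject-reported and "adjusted attack rates of attacks requiring treatment with targeted HAE medications", and refers back to 6.7.7.7 for the class.

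The protocol is wider. Inclusion criterion 5 (section 7.2.1) asks for "Access to and ability to use one or more acute medications approved by the relevant competent authority for the treatment of acute attacks of HAE". Protocol section 8 leaves families to obtain these medicines themselves; the sponsor does not supply them. SAP 8.1 places sites in North America, Israel and Europe.

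SAP 9.6 defines an 'any C1-INH' group for on-demand medication history. It contains "plasma-derived C1-INH replacement (Firazyr, Cinryze on-demand, Berinert on-demand, Kalbitor") as well as Ruconest as recombinant replacement, with fresh frozen plasma added to the plasma-derived set.

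**The concern.** A closed list of brands is applied to an open set of permitted medicines. A child may comply fully with the protocol, treat an attack with an approved acute HAE medicine, and have that attack grouped with painkillers and anti-nausea drugs. Another brand of a listed active substance would be enough to cause this.

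On-demand treatment is part of the secondary effectiveness endpoint. SAP 3.2.2 words it as the number and proportion of attacks requiring such treatment, and protocol 12.2.6 as use of on-demand rescue medication. Neither limits it to a list, yet the planned treated-attack rate tables all are. The analyses are descriptive and missing data are not imputed, so the class definition goes straight into the reported rate.

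The C1-INH group is a smaller matter. A subgroup line that coincides with the whole list gives the reader of the history tables no information.

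**Working it through.** The plan gives no figure on this point to reproduce. The check is a comparison of lists and outputs, followed by the SAP's own rate formula.

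**1. Lists.**
- Targeted (SAP 6.7.7.7): {Berinert, Cinryze, Kalbitor, Firazyr, Ruconest, fresh frozen plasma}, 6 items.
- C1-INH group (SAP 9.6): {Firazyr, Cinryze, Berinert, Kalbitor} + {Ruconest} + {fresh frozen plasma}, 6 items.
- The difference is empty in both directions. A child using any one of the six is counted as 'any C1-INH'.
- Permitted (protocol 7.2.1, criterion 5): any acute HAE medicine with the relevant approval. Nothing confines this to the six.

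**2. Outputs that use the targeted class.** The summary of targeted medication use and the treated-attack rates in SAP 12.1.5; tables 14.2.3.6.1 to .4 and 14.2.3.7.1 to .3, so 4 + 3 = 7 tables.

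**3. Outputs not tied to it.**
- Number of subject-reported attacks requiring treatment (SAP 12.1.5).
- Whether the attack was treated (SAP 12.1.4, attack characteristics; tables 14.2.3.4.x).
- Attack-level acute medication (tables 14.1.4.4.1 to .3).
- Diary and HAE medication listings (16.2.6.1.1, 16.2.4.4.3).

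**4. Size.** SAP 6.7.7.4 gives rate = number of attacks × 28 / days. Let f be the share of treated attacks in which only an unlisted approved product was used. An attack given both a listed and an unlisted product still counts, so only sole use matters:

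targeted rate = true treated rate × (1 − f).

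Assume an average of 6 treated attacks per child in 84 days (12 weeks): 6 × 28 / 84 = 2.0 per month.

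| f (assumed) | Reported rate per month |
|---|---|
| 0% | 2.0 |
| 10% | 2.0 × 0.90 = 1.8 |
| 25% | 2.0 × 0.75 = 1.5 |
| 30% | 2.0 × 0.70 = 1.4 |
| 50% | 2.0 × 0.50 = 1.0 |
| 100% | 0.0 |

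**5. Comparison of SOC with berotralstat.** The ratio of on-treatment to SOC rates is multiplied by (1 − f on treatment) / (1 − f in SOC). If f is the same in both periods, this factor is 1 and the ratio is unaffected.

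**The case against.** The best defence is that the affected tables are labelled as targeted-medication tables, while the unrestricted outputs in step 3 of the working address the endpoint as worded. This stands in part. A reader might infer that all reporting of rescue use is understated; it is not. But the unrestricted outputs are counts, characteristics and listings. No treated-attack rate table without the targeted limit is planned.

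Four further inferences are tempting and are not supported.

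- *The main adjusted attack rate loses attacks too.* SAP 6.7.7.2 says: "If the entire adjusted attack is untreated, it must have a duration > 24 hours". If 'untreated' meant without a targeted medicine, short attacks treated with an unlisted product would drop out. The sentence has no such qualifier, and the SAP writes 'targeted' elsewhere when it means it. The natural reading is no treatment at all. One clarifying sentence is warranted, and no more.
- *The rule could imitate a fall in rescue use on berotralstat.* That needs f to rise between periods: from 0 to 20%, for example, would show as a 20% fall. The documents describe no change of supply or product.
- *Some products in the C1-INH group do not belong there.* The documents do not give the active substances of the named brands, so this cannot be settled from them. Only the identity of the two lists is established, and SAP 9.6 also displays individual medications.
- *Unlisted products are in use.* The documents name none and report no use of one, so f could be zero.

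It is also true that this is a single-arm PK study of about 30 children with no hypotheses, and that no decision rule uses the targeted rate. That limits the consequences. It does not make the definition sound.

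**Conclusion.** The point holds within limits. Applied literally, SAP 6.7.7.7 leaves attacks treated only with a protocol-permitted but unlisted acute medicine out of the targeted-treatment rates in seven tables, and the understatement equals the share of such attacks. That share is unknown. The range of 1.8 to 1.4 against a true 2.0 per month rests on an assumed 10-30% and on an illustrative true rate. The other treatment summaries stand, as does the adjusted attack rate on the natural reading of 'untreated'.

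The 'any C1-INH' group in SAP 9.6 duplicates the targeted list. This affects the medication-history description only, not on-study rates. Neither matter touches the primary PK endpoint or the safety analyses. Both should be corrected before database lock.

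**What to change.** - **SAP 6.7.7.7:** define 'targeted' by WHODrug-coded active substance, whatever the brand, from one study-wide list of substances approved for acute HAE attacks, plus fresh frozen plasma. Do not tie the class to approval in each child's country, because the same product would then be targeted at one site and not at another. Review 'other' diary entries against the list before lock.
- **SAP 6.7.7.2:** state which medicines make an attack 'treated'.
- **SAP 9.6:** verify each member of the C1-INH group by active substance and re-derive the group.

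The cost is SAP wording, a code list, and coding and review of free-text 'other' entries. WHODrug coding is already planned in SAP 9.5; the team should confirm that it covers the diary treatments. No new data are needed.
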